7.7 Fourth Manuscript	23
7.8 Fifth Manuscript.....	24
7.9 Sixth Manuscript	26
References	28

Abbreviations

Abbreviation/Acronym	Definition
A1C	Glycosylated haemoglobin level
Apo B	Apolipoprotein B
ASA24-2018-Canada	Automated Self-Administered 24-Hour Dietary Assessment Tool for Canada
BMI	Body Mass Index
FoodRx	Healthy food prescription incentive program
HDL	High-Density Lipoprotein
HEFI-2019	Healthy Eating Food Index-2019
HEI-2015	Healthy Eating Index – 2015
LDL	Low-Density Lipoprotein
PIA	Perceived Income Adequacy
PROM	Patient-Reported Outcome Measures
QALY	Quality-Adjusted Life-Years
RCT	Randomised Controlled Trial
T2DM	Type 2 Diabetes Mellitus
UPF	Ultra-Processed Foods

1. Introduction¹

Type 2 diabetes (T2DM) places a tremendous burden on healthcare systems worldwide, as individuals with T2DM incur twice the healthcare costs as their age- and sex-matched counterparts.^{1, 2} The total economic costs of diabetes were CDN\$30 billion in Canada in 2019, making it among the most costly chronic conditions.³⁻⁵ The human toll on individuals and their families is also substantial in terms of diminished quality of life associated with managing T2DM.^{6, 7} Many of these human and economic costs can be mitigated by adhering to a healthy diet within an overall diabetes management plan. A healthy diet can yield clinically meaningful improvements in blood glucose levels, which can reduce diabetes complications over time.⁸⁻¹¹

The high and continually escalating costs of many healthy foods^{12, 13} represents a formidable barrier to following a healthy dietary pattern for individuals with T2DM, particularly for those who are experiencing food insecurity.¹⁴⁻¹⁷ Food insecurity, described as inadequate or insecure access to food due to financial constraints¹⁸, is a strong predictor of high-cost healthcare use.¹⁹ Evidence indicates individuals with T2DM who are experiencing food insecurity have lower diet quality than their food secure counterparts, leading to elevations in blood glucose levels,^{20, 21} and high rates of diabetes complications and acute care use.²² Indigenous groups (constitutionally recognised as First Nations, Inuit and Métis) are a population of particular concern, given their disproportionately high rates of both T2DM and food insecurity.²³ The coexistence of food insecurity and T2DM, therefore, has major implications for healthcare costs. Although the adverse impacts of food insecurity on diet quality and blood glucose levels are well documented, effective strategies to address these challenges remain limited.

2. Rationale and Objectives

Healthy food prescription programs are innovative approaches to address these adverse impacts by assisting individuals who are experiencing food insecurity to purchase diabetes appropriate foods. These programs provide financial benefits or incentives to improve access to healthy foods for populations with food insecurity and chronic conditions. Current evidence suggests these programs may improve diet quality, blood glucose levels, and other health-related outcomes, while reducing food insecurity, including within Indigenous communities.²⁴⁻²⁶ We conducted a randomized controlled trial (RCT) to investigate the effectiveness of a 12-month healthy food prescription incentive program (FoodRx program) on glycosylated hemoglobin levels (A1C; which represent average blood sugar levels over the previous 3 months.²⁷) and additional secondary and exploratory outcomes among adults with T2DM who were experiencing food insecurity.

2.1 Hypotheses

Primary Objective: To investigate the effectiveness of the FoodRx healthy food prescription incentive program in reducing A1C.

H_0 (null hypothesis): the healthy food prescription incentive program **does not** reduce A1C by a clinically meaningful difference of at least 0.5% between the intervention and comparison groups at 12-months.

H_1 (alternative hypothesis): the healthy food prescription incentive program **does** reduce A1C by a clinically meaningful difference of at least 0.5% between the intervention and comparison groups at 12-months.

Secondary and Exploratory Objectives: To investigate the effectiveness of the FoodRx healthy food prescription incentive program in reducing food insecurity, and improving clinical health markers, dietary intake, and patient-reported outcome measures (PROMs).

¹ A comprehensive study protocol has been published (doi:10.1136/bmjopen-2021-050006).

3. Methods

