4.2 Sample Size

The sample size calculation was based on A1C, the primary outcome for the RCT. A mean baseline A1C of 8.5% (SD=1.4%) was expected in our population based on local administrative data.⁴⁴ For 90% power to detect a minimally important clinical difference in A1C of 0.5%⁴⁵, 594 participants were required assuming 5% type 1 error, 30% attrition⁴⁶, and potential design effects based on sampling in different primary care clinics and communities (25% inflation).

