5.1 Primary Outcome

T2DM is a chronic metabolic disorder characterized by high blood glucose levels resulting from insulin resistance and/or impaired insulin secretion by the pancreas.⁴⁷ Monitoring blood glucose is essential to effective T2DM management. In this study, glycemic control was primarily quantified using A1C, which reflects average blood glucose levels over the previous 3 months.⁴⁸ An absolute reduction of 0.5% in A1C is achievable through improving diet quality^{8, 9} and is considered a clinically meaningful difference.⁴⁵ The 12-month FoodRx program provided adequate time to see dietary changes in 4 A1C cycles.

² *Indicates this characteristic was added after protocol registration.

The priority source for A1C will be blood samples, which participants provided at an Alberta Precision Laboratory or DynaLIFE Medical Lab of their choice. Blood sample collection and testing were standardized to the Diabetes Complications and Control Trial.⁴⁹⁻⁵² When A1C results are not available from blood samples participants' provided specifically for the RCT, we will extract A1C results from medical records and/or the Alberta Health Services' Analytics Data Integration, Measurement, and Reporting database. For extracted A1C, we will use results that were collected 3 months before or after the time point of interest (e.g., 3 months before or after the participant's post-intervention lab collection date). We will analyze 12-month A1C as a continuous outcome.

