6.2 Hypothesis Testing

For hypothesis testing, confidence intervals are set at 95% and statistical significance is set at $p < 0.05$. Confidence intervals and absolute p-values will be reported in all manuscripts, regardless of statistical significance. Adjusted and unadjusted estimates will be reported.¹⁰⁸ When interpreting results, emphasis will be placed on effect sizes, confidence intervals, and clinical relevance rather than statistical significance alone.

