6.5 Multiple Comparisons

We have used current guidelines for multiplicity to assess the risk of increased Type I error rates in this study.^{116, 117} As such, we will not adjust for multiple comparisons given the RCT 1) is exploratory, 2) includes 2 distinct treatment arms, 3) has a single pre-specified primary outcome that is the basis for statistical inference, 4) positions secondary and exploratory outcomes as supportive to the primary outcome and as hypothesis-generating, 5) did not include interim analyses, 6) will account for repeated measures using mixed-effect models with group by time and time-treatment interactions (testing for contrasts at each timepoint)¹¹⁷, 7) includes pre-specified exploratory sub-group analyses, and 8) includes exploratory sensitivity analyses to assess treatment consistency across groups. In addition, multiplicity adjustments increase the chance of type 2 errors, and assume all null hypotheses are true (i.e., all positive results are false positives). Lastly, these adjustments assume all outcomes are independent, which is not the case for the FoodRx RCT as many outcomes are related (e.g., blood lipids, systolic and diastolic blood pressure). All results will be interpreted with caution considering p-values,

confidence intervals, and effect sizes. Findings for secondary results, and secondary and exploratory outcomes will be presented as exploratory.¹¹⁸

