7.4 Primary Manuscript

This paper will report results for 12-month A1C, our primary outcome, along with secondary and exploratory outcomes at 6-, 12-, and/or 18-months, including blood glucose levels, clinical health markers, and need for antihyperglycemic medication.

12-month A1C, Primary Outcome

We will assess the intention to treat effect of group assignment on mean A1C at 12-months as a continuous outcome using mixed-effects linear regression. The primary test will be the group \times time interaction contrast at 12-months (i.e., post-intervention), which estimates between-group differences in mean A1C from baseline to 12 months. Models will be adjusted for baseline A1C to estimate treatment effect while holding baseline A1C constant, and additional blocking variables (gender, recruitment location). To improve the precision of effect estimates, models will also be adjusted for age, race/ethnicity, educational attainment, number of children living in the home, and diabetes duration. Additionally, all models will include a data source indicator variable (study measured vs administrative health data), group (FoodRx vs comparison), collection timing (number of days measurement was taken since baseline), and restart cohort indicator variable (did not restart vs did restart). We will include random intercepts for participants (participant study ID) to account for within-subject correlation due to repeated measures, and for primary care clinics (clinic study ID) to account for clustering of participants within clinics. Missing data for covariates will be addressed using full information maximum likelihood.

We will conduct subgroup analyses for 12-month A1C by baseline household food insecurity severity (marginal, moderate, severe), gender (man, woman, gender diverse), recruitment location (urban setting, rural setting, Indigenous primary care clinic), Indigenous identity, baseline A1C ($\leq 8.5\%$, $\geq 8.6\%$), and baseline insulin use (no, yes).

We will conduct dose-response analyses to examine whether 12-month A1C differs based on the total value of incentives redeemed, a continuous variable, in the first 6 months for the mid-intervention analysis, and in the full 12-months for the post-intervention analysis.

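### The written hypotheses put the null boundary at a 0.5% A1C reduction, but the primary test and sample size fit a null of zero, so a significant result would not establish the stated H1

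*SAP*

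**What the plan says.** - **Section 2.1, objective.** The primary objective is "To investigate the effectiveness of the FoodRx healthy food prescription incentive program in reducing A1C", with no margin.
- **Section 2.1, hypotheses.** Directly below, H0 says the program does not, and H1 that it does, "reduce A1C by a clinically meaningful difference of at least 0.5% between the intervention and comparison groups at 12-months".
- **Section 4.2.** The sample size is set "For 90% power to detect a minimally important clinical difference in A1C of 0.5" percent, with SD 1.4%, 5% type 1 error, 30% attrition and 25% inflation for design effects, giving 594. Sidedness and the null value are not stated.
- **Section 5.1.** "An absolute reduction of 0.5% in A1C is achievable through improving diet quality", and the same section calls this size clinically meaningful.
- **Section 7.4.** The primary test is the group by "time interaction contrast at 12-months (i.e., post-intervention), which estimates between-group differences in mean A1C from baseline to 12 months". The model adjusts for baseline A1C. No non-zero null value is named.
- **Section 6.2.** "confidence intervals are set at 95% and statistical significance is set at" p < 0.05. On interpretation, "emphasis will be placed on effect sizes, confidence intervals, and clinical relevance rather than statistical significance alone".
- **Section 6.5.** The trial "has a single pre-specified primary outcome that is the basis for statistical inference".

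**The concern.** The two hypotheses are complementary around 0.5%, so a true reduction of 0.3% or 0.4% lies inside H0, and rejecting H0 asserts a reduction of at least 0.5%. The test that the rest of the SAP describes looks like an ordinary test of no difference. If so, three things follow.

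- Rejecting the null that is tested does not establish the H1 that is written.
- The 5% type 1 error does not apply to the written H0.
- The 90% power does not apply to the written H1. A true effect of 0.5% cannot be both the boundary of the null and the effect that the trial is powered to detect.

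This is the SAP's only formal statement of the primary hypothesis, and Section 6.5 rests statistical inference on that one outcome. The risk is that a significant result is read as proof of a clinically meaningful reduction.

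**Working it through.** All A1C differences are absolute, in the SAP's percent units.

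**Inputs.** Difference 0.5, SD 1.4, power 90%, alpha 5%, attrition 30%, inflation 25%, total 594 (Section 4.2). Allocation 1:1, with 299 and 297 randomised (Section 3.4). The SAP gives no correlation between baseline and 12-month A1C; 0.5 to 0.7 is assumed below.

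**1. Reproduce the sample size with a null of zero.**

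n per arm = 2 × (z for alpha + z for power)² × SD² / difference²

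- Two-sided 5%: 2 × (1.960 + 1.282)² × 1.4² / 0.5² = 164.8. The t-test version gives 165.7, rounded up to 166. Then 166 × 1.25 / 0.7 = 296.4, rounded up to 297; × 2 = **594**, as stated.
- One-sided 5%: 134.3, rounded up to 135. Then 135 × 1.25 / 0.7 = 241.1, rounded up to 242; × 2 = 484, which does not match.
- With the null boundary at 0.5 and a true effect of 0.5, the distance from the null is zero, so no finite sample size gives 90% power.

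**2. Where the planned test becomes significant (unadjusted).**

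- SE = 1.4 × √(2/166) = 0.154. With the 299 and 297 actually randomised and the same attrition and inflation, SE = 0.153.
- Threshold = 1.96 × 0.154 = 0.30. At that estimate the 95% CI runs from about 0 to 0.60.

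**3. How often it is significant while the written H0 is true.**

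P(significant) = 1 − Φ(1.96 − d/SE)

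| True reduction d | P(significant) | Written hypothesis that is true |
|---|---|---|
| 0.30 | 50% | H0 |
| 0.40 | 74% | H0 |
| 0.50 | 90% | H1 (at the boundary) |

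**4. What rejecting the written H0 would take.**

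- The observed reduction would have to reach 0.5 + 1.96 × 0.154 = 0.80 (two-sided 5%).
- Power of that test is 2.5% at a true reduction of 0.5, 50% at 0.8 and 90% at 1.0. The SAP proposes no true effect above 0.5; these values are a range for illustration.

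**5. Adjustment for baseline A1C.**

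Adjusted SE = 0.154 × √(1 − r²)

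| Assumed r | SE | Significant from | P(significant) at true 0.40 |
|---|---|---|---|
| 0.5 | 0.133 | 0.26 | 85% |
| 0.7 | 0.110 | 0.22 | 95% |

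A significant result can have its whole 95% CI below 0.5 when 2 × 1.96 × SE < 0.5, that is SE < 0.128, or r above about 0.56. At r = 0.7 this happens for observed reductions of about 0.215 to 0.285. Such a result rejects zero and is also evidence against the written H1.

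**The case against.** - **The zero null is inferred.** Section 7.4 names no null value and p < 0.05 fits any null. This is right. The inference rests on the unshifted contrast, the lack of any margin in Sections 6.2 and 7.4, and the exact match with 594. The opposite reading, a test against 0.5%, appears nowhere and is incompatible with the sample size.
- **No wrong conclusion is planned.** No passage says that p < 0.05 will be reported as a reduction of at least 0.5%. Section 6.2 requires confidence intervals and p-values whatever the significance, and stresses effect sizes and clinical relevance. Section 6.5 asks for cautious interpretation and calls the trial exploratory. This stands as real mitigation, but it is general. It gives no rule for reading the result against 0.5%, and it does not alter H0 or H1.
- **The 50% and 74% are ordinary power against zero.** They are error rates only if a significant result is taken to reject the written H0. That is correct, and it is why the point concerns the wording and not the test.
- **The case of a whole interval below 0.5% depends on an assumed correlation and covers a narrow range.** True; it is an illustration only.
- **Rewording now lowers the written bar and removes its direction.** Recruitment ended in December 2023 (Section 4.1) and analysis was planned from fall 2025 (Section 4.4). This bears on how the change is made and recorded. It is not a reason to leave the mismatch.

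**Conclusion.** The concern holds. Section 2.1 states a hypothesis with a 0.5% margin, while the sample size, and by inference the primary test, are for a null of zero. At the planning values a significant result needs an observed reduction of only about 0.30%, against about 0.80% to reject the H0 that is written. The planned test would be significant in about 74% of trials at a true reduction of 0.40%, inside that H0. These figures assume SD 1.4%, 30% attrition, the 1.25 inflation and no gain from adjustment. Adjustment at an assumed correlation of 0.5 to 0.7 lowers the significance threshold to 0.26% to 0.22%.

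The sample size and power are correct for a zero null, and the model and estimate are not in question. Only the two hypothesis sentences are out of line. The point should be fixed because it decides what a significant primary result may be said to show.

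**What to change.** **Section 2.1.** Restate H0 as no difference between FoodRx and comparison in mean 12-month A1C, and H1 as a difference, tested two-sided at 5%. Describe 0.5% as the difference that the trial has 90% power to detect and as the benchmark for clinical interpretation, which agrees with Sections 4.2 and 5.1.

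**Section 6.2.** Add that p < 0.05 alone does not establish a reduction of at least 0.5%, and that the estimate and its 95% CI will be reported against 0.5%.

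**Record.** Make this a dated amendment with a reason, before the primary analysis and checked against the published protocol. If results have already been seen, disclose that.

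**Alternative.** If the sponsor wants to keep the claim of at least 0.5%, the primary test should compare the confidence limit with 0.5%. That needs a new sample size justification: with 594 participants, unadjusted power is 2.5% at a true 0.5% and reaches 90% only at about 1.0%.

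**Cost.** The first option changes wording only; sample size, model, estimate, CI and p-value stay as they are. The price is that a clinically meaningful effect can no longer be inferred from significance alone.

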3.1 Study Design

The FoodRx study was a parallel-group pragmatic RCT. Participants were assigned to a healthy food prescription incentive intervention group or a healthy food prescription-only comparison group. This study was conducted in accordance with the Tri-Council Policy Statement and the Declaration of Helsinki. Ethical approval was obtained from the Conjoint Health Research Ethics Board at the University of Calgary (REB20-0543; Calgary, Alberta, Canada), and the Research Ethics Office at the University of Alberta (Pro00107116; Edmonton, Alberta, Canada). This study is described in accordance with the TIDieR Checklist²⁸ and the CONSORT statement²⁹⁻³¹. The study was preregistered in the clinicaltrials.gov database (NCT04725630) and the full study protocol has been published elsewhere³².

3.2 Intervention and Frameworks

The FoodRx program consisted of 2 core elements. The first element was a one-time healthy food prescription designed to resemble current diabetes nutrition education by outlining a diabetes-appropriate dietary pattern. It was a low literacy resource with minimal text and colourful images. The information included a prescription for a healthy eating pattern, diabetes-relevant dietary tips (e.g., drink water when thirsty), a diabetes-appropriate recipe, community resource links, and emergency food assistance information tailored to each participant's community. Clinical research nurses from the FoodRx project team and the University of Alberta's Quality Management in Clinical Research Unit explained the healthy food prescription to all participants at baseline (0 months). As the prescription mimicked current standard of care, it was expected to have minimal influence on the dietary patterns of participants within the context of acute financial barriers.³³⁻³⁸

The second element was a weekly healthy food incentive of CDN\$10.50 per household member for 12 months. Participants earned the weekly incentive by purchasing whole, minimally processed foods with little to no added fat, sugar, or salt from all food groups in study-affiliated supermarkets, which were part of a large chain with multiple banners and locations.^{8, 39} Incentive-eligible foods included dairy products; whole grain bread, pasta, and cereal; fresh, frozen, and canned vegetables; fresh and frozen fruit; fresh, plain meats, fish, and poultry; canned fish and meat alternatives (eggs, canned and dried beans, plain almonds). Researchers calculated incentive amounts based on total household size as reported at baseline (0 months), which was communicated to participants after randomization. Once participants reached their spending threshold as defined by their household size, they immediately received loyalty card points equal to their eligible spending (e.g., a two-person household spending CDN\$21 received CDN\$21 in points). The incentive was capped at CDN\$10.50 per person per week, and points were only given to households that met or exceeded their threshold each week. Although progress towards meeting the minimum spend was reset weekly, earned points carried over between weeks, did not expire, and could be redeemed for anything in-store in CDN\$10 increments. However, participants were encouraged to use these points to continue the earn-reward cycle by purchasing incentive-eligible foods. At baseline, participants' loyalty cards were preloaded with points equivalent to one week's incentive amount to allow initial participation without paying out-of-pocket. The incentive redemption mechanism was pilot tested⁴⁰ and is fully described elsewhere.³²

3.3 Data Collection Schedule and Data Sources

Participants in both groups completed data collection at baseline (0-months), mid- (6-months), and post-intervention (12-months with data collection beginning 2 weeks prior to participants' program end date). Participants completed a self-administered online questionnaire in REDCap⁴¹, 2 online 24-hour dietary recalls using the Automated Self-Administered 24-Hour Dietary Assessment Tool for Canada (ASA24-2018-Canada)⁴², and biochemical and physical measurements (e.g., blood samples, height, weight, skin carotenoids) as per the schedule in Figure 1.

[figure not shown]

Figure 1: Data Collection Schedule

3.4 Randomization and Blinding

Prior to randomization, participants completed baseline data collection and received the healthy food prescription. Researchers randomized participants to either the FoodRx (n=299) or comparison (n=297) group with a 1:1 allocation ratio using a computer-generated, concealed, blocked randomization sequence in REDCap (Research Electronic Data Capture)⁴¹ created by an independent statistician. Blocking variables included gender identity (woman, man), recruitment location (urban setting, rural setting, Indigenous primary care clinic), and baseline A1C (6.5-8.5%, 8.6-12%). The intervention group received both a healthy food prescription and a healthy food incentive. The comparison group received a healthy food prescription alone.

Due to the nature of the intervention, participants were not blinded to their allocation; however, they were blinded to study objectives. Participants in the comparison group were also blinded to the details of the healthy food incentive, including its monetary value and eligible foods. Care providers and researchers who collected and analyzed the data were blinded to treatment allocation with the exception of a research assistant who assisted participants in the intervention group throughout the trial.

4. Trial Population

